#### **4.3. Pharmacokinetic Analysis Set**

The PK analysis set will include all subjects who received FT-4101 with sufficient evaluable PK concentration data appropriate for the evaluation of interest without major protocol deviations or violations that would have an impact on the absorption, distribution, metabolism, or excretion. The PK analysis set will be used for analysis of PK endpoints.

#### **4.4. Preliminary Efficacy Analysis Set**

The Preliminary Efficacy analysis set will include all subjects who received FT-4101 or placebo with baseline and at least one quantifiable post baseline MRI-PDFF without major protocol deviations or violations that would have an impact on PD (Specifically MRI-PDFF). The Preliminary Efficacy analysis set will be used for analysis of MRI-PDFF endpoints.

#### **4.5. Pharmacodynamic Analysis Set**

The PD analysis set will include all subjects who received FT-4101 or placebo without major protocol deviations or violations that would have an impact on PD. The PD analysis set will be used for analysis of PD endpoints.

### **5. INTERIM ANALYSIS**

No interim analysis is planned.

## **6. STATISTICAL METHODS OF DATA ANALYSIS**

### **6.1. General Considerations**

Unless otherwise specified, all data will be provided in subject level listings in addition to summary tables or figures.

#### **6.1.1. Statistical Notation and Presentation**

Continuous data will be summarized in tables using the number of subjects (n), mean, median, standard deviation (SD), minimum and maximum. For PK concentration and parameter data, the geometric mean, and its standard error and coefficient of variation (CV%) of geometric mean will be provided as well. Categorical data will be summarized by count and percentage. The denominator will be the number of subjects or the number of records, whichever is more appropriate.

Minimum and maximum values will use the precision of the original value in the database. Means, least squares (LS) means, and medians will be rounded to one decimal place greater than the precision of the original value. Estimates of SE, SD and the 90% confidence intervals will be rounded to two decimal places greater than the precision of the original value. Percentages will

be rounded to the nearest tenth digit. P-values will be presented with four decimal places, and p-values less than 0.0001 will be presented as <.0001.

### **6.1.2. Hypothesis Testing and Multiplicity Adjustment**

The primary preliminary efficacy endpoint will be tested using a one-sided test at an alpha level of 0.05. The null hypothesis and alternative hypothesis are presented below.

$$H_0: \text{Diff} \geq 0$$

$$H_a: \text{Diff} < 0$$

Where Diff is the mean difference: FT-4101 minus Placebo.

If more than one dose of FT-4101 is evaluated, control of the alpha level will be accomplished using Holm's Sequential Bonferroni procedure to test each FT-4101 dose against the pooled placebo subjects. There will be two comparisons.

The p-values of the multiple comparisons will be ordered from smallest to largest. The corrected p-value from each comparison, starting from the smallest original p-value, will be calculated based on the following formula:

$$p_{\text{Bonferroni},i|C} = (C - i + 1) * p$$

where the number of comparisons is  $C$ , index  $i$ , ranges from 1 to  $C$ , and the original p-value that is to be corrected,  $p$ . Corrected p-values less than 0.05 will be considered statistically significant.

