#### 12.5.1.1 Liver Fat Assessed by MRI-PDFF at 12 weeks

The observed values and the change (absolute) from baseline and the percent change from baseline of liver fat estimated from MRI-PDFF will be analyzed descriptively by treatment group and visit.

Change at Week 12 (absolute and relative) in percentage of liver fat as assessed by MRI-PDFF will be analyzed by a Wilcoxon rank-sum test. The test will be one-sided and use a significance level of 0.05. Subjects in each dose group will be tested against the pooled placebo subjects from each cohort.

If more than one dose of FT-4101 is evaluated, control of the alpha level will be accomplished using Holm's Sequential Bonferroni procedure [Holm 1979] to test each FT-4101 dose against the pooled placebo subjects.

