#### **6.10.1.1. Reduction of Liver Fat Assessed by MRI-PDFF at 12 Weeks**

The observed values and the change from baseline and the percent change from baseline of liver fat estimated from MRI-PDFF will be summarized descriptively by visit and treatment group.

The change and percent change at Week 12 in liver fat (%) as assessed by MRI-PDFF will be analyzed by a Wilcoxon-Mann-Whitney test. The test will be one-sided and use a significance level of 0.05. Subjects in each dose group will be tested against the pooled placebo subjects from each cohort.

Multiplicity adjustment to control the alpha level will be accomplished using Holm's Sequential Bonferroni procedure as previously described.

If change or percent change of MRI-PDFF is not obvious deviated from symmetric distribution, a two-sample independent t-test will be carried out to compare liver fat (%) between FT-4101 treatment and the pooled placebo as supportive analysis, based on one-sided significance level of 0.05. P value will be corrected using Holm's Sequential Bonferroni procedure as previously described.

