#### **6.10.2.1. Reduction of Liver Fat Assessed by MRI-PDFF at 6 Weeks**

The reduction of liver fat assessed by MRI-PDFF at 6 Weeks will be analyzed similar to the primary preliminary efficacy endpoint.

A supportive analysis using a mixed effects model with repeated measures (MMRM) will be used to analyze the change from baseline, both absolute change and percent change (absolute and relative), to week 6 and week 12; the model will include change in liver fat (%) on MRI-PDFF (absolute and relative) as dependent variable, treatment group as independent variable, covariates including baseline liver fat (%), visit, interaction term of treatment and visit, and a random slope and intercept per subject. Model parameters will be estimated using the restricted maximum likelihood method (REML). An unstructured covariance matrix will be used to estimate the intercept-slope covariance. In case of convergence problem, other covariance structure will be used in the order of compound symmetry and variance component. The least squares (LS) means and their corresponding 90% confidence intervals and p-values at one sided test will be presented. The LS mean difference between treatment groups will be presented along with the 90% confidence interval and p-value.

The following SAS code will be used for the MMRM analysis:

```
Proc mixed method=reml;
  Class usubjid visit treat;
  Model change [or percentchange] = baseline visit treat
  treat*visit /ddf=kr solution alpha=0.05;
  repeated visit /subject=usubjid type=un;
Run;
```

Where treat=treatment group (pooled placebo, FT4101 3.0 mg, FT 4101 4.5 mg), baseline = baseline liver fat (%), change = absolute change in liver fat (%) from baseline, percentchange = relative percent change in liver fat (%) from baseline, visit=study visit (Week 6, Week 12), usubjid = subject ID.

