#### **6.10.2.2. Proportion of Subjects with $\geq 30\%$ Relative Reduction in Liver Fat at Week 12 Assessed by MRI-PDFF**

The proportion of subjects experiencing a relative reduction of 30% or greater of liver fat at week 12 as assessed by MRI-PDFF will be summarized descriptively and analyzed using a Fisher's exact test. Subjects in each dose group will be compared to the pooled placebo subjects

from each cohort. P-values will be corrected using Holm's Sequential Bonferroni procedure as previously described.

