## **7. CHANGES TO THE PLANNED ANALYSIS IN THE PROTOCOL**

Two-sample independent t-test will be carried out to compare liver fat (%) between FT-4101 treatment and the pooled placebo at 6 and 12 weeks as a supportive analysis, based on one-sided significance level of 0.05.

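### SAP 6.1.2 names Holm's procedure but writes a rule without its stopping step, so the two disagree when both raw p-values lie in [0.025, 0.05)

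*SAP*

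**What the plan says.** Protocol 12.5.1.1 states: "If more than one dose of FT-4101 is evaluated, control of the alpha level will be accomplished using" Holm's procedure, with a literature citation. It writes out no steps, and neither does the Study Summary.

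SAP 6.1.2 also names Holm ("Sequential Bonferroni procedure to test each FT-4101 dose against the pooled placebo subjects. There will be two comparisons") and then gives the mechanics. The p-values are ordered from smallest to largest. "The corrected p-value from each comparison, starting from the smallest original p-value, will be calculated based on the following formula": (C − i + 1) × p, where C is the number of comparisons and i the rank. The decision rule is "Corrected p-values less than 0.05 will be considered statistically significant".

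The same rule is used elsewhere in the SAP:

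- Section 6.10.1.1, primary Week 12 test: "Multiplicity adjustment to control the alpha level will be accomplished using" Holm. The supportive t-test in that section gets the same correction.
- Section 6.10.2.1, Week 6 liver fat: "will be analyzed similar to the primary preliminary efficacy endpoint".
- Section 6.10.2.2, the 30% responder test: p-values are corrected by the "Sequential Bonferroni procedure as previously described".

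SAP section 7 lists one change from the protocol ("Two-sample independent t-test will be carried out to compare liver fat" between groups) and declares no departure from Holm.

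**The concern.** Holm's procedure is step-down. If the smallest p-value fails its threshold, testing ends and no other comparison can be significant. In terms of adjusted p-values, a later one can never be smaller than an earlier one. SAP 6.1.2 has the right multipliers but lacks that condition. Starting from the smallest p-value fixes the order of calculation; it does not make the second verdict depend on the first.

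A programmer who codes the formula and a colleague who calls a standard Holm routine would both be following the SAP, yet they could report different primary dose conclusions from the same data. Where they differ, the written rule favours the dose with equal or weaker evidence. When the two p-values are equal, the formula does not say which dose is i = 1, so identical results can get opposite verdicts.

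**Working it through.** **Inputs.** C = 2 comparisons and one-sided alpha 0.05 (SAP 6.1.2); 10 evaluable subjects per group, difference 20, SD 14, so the planned effect is 20/14 = 1.43 SD (SAP 3.4). The plan gives no figure for the multiplicity rule itself. Its 84% power did not reproduce: the exact test, simulated at one-sided 0.05, gives 89.8%. That is a separate matter, and nothing below depends on it.

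**The two rules.** Let p(1) ≤ p(2).

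- Written rule: corrected values are 2·p(1) and 1·p(2), each compared with 0.05.
- Holm: adjusted values are 2·p(1) and max(2·p(1), p(2)).

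They differ only when 2·p(1) ≥ 0.05 and p(2) < 0.05, that is, when both raw p-values lie in [0.025, 0.05). On a grid of step 0.001 they differ at all 625 points in that square and nowhere else.

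**Wilcoxon, 10 v 10.** The exact lower-tail probabilities are:

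| U | 23 | 24 | 25 | 26 | 27 | 28 |
|---|---|---|---|---|---|---|
| p | 0.0216 | 0.0262 | 0.0315 | 0.0376 | 0.0446 | 0.0526 |

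Four attainable values (U = 24 to 27) fall in the conflict band. Take U = 25 for one dose and U = 27 for the other:

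| Version of the test | Written rule: U = 25, U = 27 | Holm: U = 25, U = 27 |
|---|---|---|
| Exact | 0.0630, **0.0446** | 0.0630, 0.0630 |
| Normal approximation | 0.0588, **0.0410** | 0.0588, 0.0588 |
| With continuity correction | 0.0640, **0.0445** | 0.0640, 0.0640 |

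Bold marks the values declared significant. The conflict does not depend on how the p-value is computed.

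**Responder test, 10 v 10.**

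- One-sided Fisher, placebo 0/10 and both doses 4/10: p = C(10,4)/C(20,4) = 210/4845 = 0.0433 for each dose. Corrected values are 0.0866 and 0.0433.
- The SAP does not state sides. Two-sided, 0/10 v 5/10: p = 2 × 252/15504 = 0.0325 for each dose. Corrected values are 0.0650 and 0.0325.

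In the one-sided test at most one dose count per placebo count falls in the band (placebo v dose: 0 v 4, 1 v 6, 2 v 7, 3 v 8, 4 v 9, 6 v 10). Every one-sided conflict is therefore a tie.

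**Frequency.** 400,000 simulated trials per scenario; normal data, 10/10/10 with a shared placebo group, exact one-sided Wilcoxon:

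| True effects of the two doses (SD) | Rules disagree | Larger p wins outright | Ties |
|---|---|---|---|
| 0, 0 | 0.20% | 0.15% | 0.05% |
| 0.7, 0.7 | 1.92% | 1.43% | 0.49% |
| 1.0, 1.0 | 2.17% | 1.62% | 0.56% |
| 1.43, 1.43 (planned) | 1.08% | 0.81% | 0.27% |
| 1.0, 1.43 | 1.26% | 0.95% | 0.31% |

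At a 2% rate the Monte Carlo standard error is √(0.02 × 0.98/400,000) = 0.02 percentage points. With the normal approximation, the rates for two active doses are 0.9% to 2.1%.

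**Error control.** Under the global null the chance of any claim is 4.14% for the written rule and 3.94% for Holm. With one null dose and the other at 1.0 SD, the chance of a claim for the null dose is 4.29% against 4.21%. All are below 5%.

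**The case against.** The strongest reply is that the name governs. Both documents say Holm repeatedly, the protocol cites the source, the multipliers are Holm's, and ordering from the smallest p-value is step-down language. Section 7 declares no departure, so 6.1.2 can be read as Holm in shorthand, and a standard routine would give the right answer. This is fair: the text does not show that the wrong rule will be run. But the SAP's decision sentence judges each corrected p-value separately, and no other section supplies the missing condition, so following it literally is also compliant.

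The remaining points limit the size of the problem without removing it:

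- Disagreement is rare, about 1% at the planned effects.
- Familywise error is kept. The written rule makes at least one claim exactly when Hochberg's procedure does, and that procedure controls error under the positive correlation a shared placebo produces.
- The trial is a proof-of-concept study with a preliminary efficacy endpoint, and escalation to Cohort B rests on safety.
- The responder example is a tie on a secondary endpoint.
- Cohort B may not run.

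**Conclusion.** The concern holds. The method named and the rule written in SAP 6.1.2 are not the same procedure, and they give different dose conclusions whenever both raw p-values lie in [0.025, 0.05). That interval is exact, given the SAP's strict inequality. If the written rule is followed, the chance of a non-Holm conclusion on the primary test is about 1% to 2% in the scenarios run with two active doses and 0.2% with none. These rates assume 10 evaluable subjects in each of three groups, normal data, and both doses evaluated.

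The choice of Holm is sound. The fault is in how it is written down, and it reaches the primary dose comparison and each analysis that borrows the rule. It should be corrected before unblinding, so that the choice between readings is not made with the results in view.

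**What to change.** In SAP 6.1.2, complete the formula with a running maximum and a cap at 1:

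- adjusted p(1) = min(1, 2·p(1))
- adjusted p(2) = max(adjusted p(1), p(2))

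Alternatively, keep the formula and add: *Testing stops at the first corrected p-value of 0.05 or more, and all remaining comparisons are declared not significant.*

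Either form restores the procedure that both documents name. It also settles ties: two equal p-values both become 2p and get the same verdict. The sections that refer back to 6.1.2 need no edit.

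The cost is one sentence in the SAP. Data collection, sample size, the named method and the protocol are unchanged.

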### **6.1.3. Study Baseline**

Unless otherwise specified, baseline will be defined as the last non-missing pre-dose measurement.

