### 9.1.17.5 De Novo Lipogenesis (DNL) Assessment

Steady state contribution of fractional DNL to plasma triglyceride (TG) palmitate (representing hepatic DNL) and sebum fatty acids (e.g. palmitate and/or sapienic acid) will be determined using mass isotopomer distribution analysis (MIDA). For the assessment of fractional hepatic DNL during the study, subjects need to be in fasting conditions (no food or drink, except for water for 10 hours prior). Fasting is not required for the assessment of sebum DNL. A 2-week deuterated water labeling approach will be used to allow fully labeling of newly synthesized fatty acids (DNL) in liver triglycerides and sebum. Multiple blood and sebum samples will be collected throughout the assessment period for the measurement of deuterium enrichment in fatty acids and body water.

Sampling time points on different days should be at approximately the same clock time. For details please see the Operations Manual.

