#### **6.10.3.1. Change from Baseline in Fasting Hepatic De Novo Lipogenesis**

Multiple blood samples will be collected at C1D-11, C1D-7, and C1D1 and post-dose at C4D4, C4D8, C4D15, and C4D22 to measure deuterium enrichment in plasma body water and plasma triglyceride-palmitate. Fractional DNL will be determined by the quantification of newly synthesized palmitate through the DNL pathway in blood sampled in the fasting state after two weeks labeling period.

Fractional hepatic DNL (%) and its absolute and percentage changes from baseline will be summarized by visit and treatment group. P value from one-sided Wilcoxon-Mann-Whitney test at significance level of 0.05 will be provided. In addition, the change from C4D15 to C4D22 will be presented to evaluate rebound of DNL.

A MMRM model will be used to analyze the absolute change in fraction of fasting hepatic DNL from baseline; the model will include change in fraction of fasting hepatic DNL from baseline as dependent variable, treatment group as independent variable, baseline fraction of fasting hepatic DNL and visit and interaction term of treatment and visit as covariate, and a random slope and intercept per subject. Model parameters will be estimated using REML. An unstructured covariance matrix will be used to estimate the intercept-slope covariance. In case of convergence problem, other covariance structure will be used in the order of compound symmetry and variance component. The LS mean and standard error and its corresponding 90% confidence intervals and p-values will be presented for each post-baseline visit. The LS mean difference between treatment and placebo will be presented along with its 90% confidence interval and the p-value for each post-baseline visit. Similar SAS code as described in Section 6.10.2.1 will be used.

Line plots of the fraction of fasting hepatic DNL (mean  $\pm$  SD) will be plotted over time by treatment group for both pre-dose (C1D-11, C1D-7, and C1D1) and post-dose (C4D4, C4D8, C4D15, and C4D22); they will be overlaid to allow visual comparison.

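### Hepatic DNL has no baseline of its own, so C1D1 (labeling day 14) serves visits at labeling days 3, 7 and 21, and their within-arm changes may partly reflect labeling time

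*SAP*

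**What the plan says.** SAP 6.1.3 sets a default that holds unless another rule is given: "baseline will be defined as the last non-missing pre-dose measurement". SAP 6.10.3.1 gives no other rule for hepatic DNL. It lists run-in samples at C1D-11, C1D-7 and C1D1, and samples "post-dose at C4D4, C4D8, C4D15, and C4D22 to measure deuterium enrichment in plasma body water and plasma triglyceride-palmitate".

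The same section plans three numerical outputs that use these visits:
- "Fractional hepatic DNL (%) and its absolute and percentage changes from baseline will be summarized by visit and treatment group".
- A mixed model for absolute change: "The LS mean and standard error and its corresponding 90% confidence intervals and p-values will be presented for each post-baseline visit".
- "In addition, the change from C4D15 to C4D22 will be presented to evaluate rebound of DNL".

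C1D-11 and C1D-7 otherwise appear only in line plots that lay the run-in series over the cycle 4 series.

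Both documents treat labeling time as part of the measurement. Protocol 9.1.17.5 states: "A 2-week deuterated water labeling approach will be used to allow fully labeling of newly synthesized fatty acids (DNL". SAP 6.10.3.1 says that fractional DNL is quantified "in blood sampled in the fasting state after two weeks labeling period". Protocol 12.5.3.1 leaves the detailed derivation of DNL and its inhibition to the SAP. The SAP gives no formula.

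**The concern.** If newly made palmitate is not fully labeled at day 3 or day 7, a value from those days differs from a day-14 value in the same subject with no change in lipogenesis. Using one day-14 baseline for every visit puts that difference into the change score. A placebo subject could then show an apparent fall at C4D4, and the FT-4101 arms would carry the same offset on top of any drug effect. The planned rebound, C4D15 to C4D22, compares day 14 with day 21 and has the same weakness within an arm.

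At stake is the reading of the single-arm results: the change tables, the percent changes, and the LS means with their own p-values. Reduced hepatic DNL is the drug's proposed mechanism (Protocol 4.1), so a reader may take a within-arm fall as evidence of target engagement.

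**Working it through.** **Step 1. Labeling days.** Intake starts on C1/D-14 and C4/D1 and lasts seven days each time (Protocol 8.5.1, Table 9-2). Appendix A places D-1 on the day before D1, so there is no day 0. Days since first intake:
- Run-in: C1D-11 = 3, C1D-7 = 7, C1D1 = 14.
- Cycle 4: C4D4 = 3, C4D8 = 7, C4D15 = 14, C4D22 = 21.

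The 14 days at C1D1 and C4D15 reproduce the plan's two-week labeling period.

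**Step 2. Which sample is baseline.** DNL blood is drawn before study drug on dosing days (Appendix A), so C1D1 is the last pre-dose value when present. The labeling-time gaps to C1D1 are 3 - 14 = -11, 7 - 14 = -7, 14 - 14 = 0 and 21 - 14 = +7 days. If C1D1 is missing, the rule takes C1D-7, and the gap at C4D15 becomes 14 - 7 = +7 days. No kinetic assumption enters so far.

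**Step 3. Possible size.** The documents give no turnover rates, so these are assumptions: constant body-water enrichment, no drug effect, and a first-order labeled fraction f(t) = 1 - 2^(-t/h) with half-time h. The apparent change from C1D1 is f(t)/f(14) - 1. The fallback error at C4D15 is f(14)/f(7) - 1.

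Example, h = 2: f(3) = 0.646, f(7) = 0.912, f(14) = 0.992, f(21) = 0.999. C4D4 gives 0.646/0.992 - 1 = -34.8%.

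| h (days) | f(14) | C4D4 | C4D8 | C4D22 | C4D15 vs C1D-7 |
|---|---|---|---|---|---|
| 0.5 | 100% | -1.6% | 0.0% | 0.0% | 0.0% |
| 1 | 100% | -12.5% | -0.8% | 0.0% | +0.8% |
| 2 | 99% | -34.8% | -8.1% | +0.7% | +8.8% |

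These half-times label at least 99% by day 14, which fits the protocol's premise of full labeling.

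**Step 4. Between-arm comparison.** All arms follow one labeling schedule, so with no drug effect the expected difference from placebo is zero at every visit. With a true DNL of 100, 50% inhibition and the same turnover in both arms, the absolute contrast is -50 × f(t), whichever baseline is subtracted. At day 3 that is -49.2, -43.8 and -32.3 for h = 0.5, 1 and 2. At day 7 it is -50.0, -49.6 and -45.6. The early contrast is diluted toward zero and is not biased toward a false effect.

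**The case against.** - **The assay may already correct for labeling time.** Protocol 9.1.17.5 names mass isotopomer distribution analysis (MIDA), body-water enrichment is sampled, and details are referred to an Operations Manual that is not available here. This may reduce or remove the offset. It stands as a reason to say *may*. However, Protocol 12.5.3.1 names the SAP as the place for the derivation, and the SAP shows no such correction.
- **DNL may be meant only at two weeks.** The sentence on the two-week period can be read that way. Yet the same section plots the DNL fraction at C4D4, C4D8 and C4D22 and reports each post-baseline visit.
- **The overlaid plots already compare like with like.** They let a reader compare days 3, 7 and 14 by eye, which is useful. They do not correct the tables or the model.
- **Placebo cancels the offset.** This is right for the between-arm null. It does not protect single-arm LS means and their p-values, or a rebound read within one arm.
- **Matching may add as much error as it removes.** Under the same model, the ±1-day windows could pair day 2 with day 4: -6% or +6% at h = 0.5, -20% or +25% at h = 1, -33% or +50% at h = 2. These are worst cases for single subjects, while the present offset is systematic. The point stands as a limit on the fix.

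A reader might go further and infer that the within-arm changes cannot be read as inhibition at all. The documents do not support that: with fast turnover the offset is 0 to -2%. Nor do they support the largest figures that the model can produce. A 7-day half-time gives -66% at C4D4, +17% at C4D22 and +50% under the fallback, but it labels only 75% by day 14 (91% for a 4-day half-time), against the full-labeling premise.

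**Conclusion.** The point holds in a limited form and is minor. The mismatch in labeling days at C4D4, C4D8 and C4D22, and the loss of the match at C4D15 when C1D1 is missing, follow from the two documents alone. Whether it distorts the results, and by how much, does not.

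Under constant enrichment and half-times of 0.5 to 2 days, only C4D4 is affected materially (about -2% to -35%). C4D8 moves by 0 to -8%, C4D22 by at most +1%, and C4D15 under the fallback by at most +9%. By this measure the rebound is barely touched.

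The constant-enrichment assumption is fragile, because intake stops after seven days. If body water rises and then decays (assumed half-life 7 or 10 days, h from 0.5 to 7), C4D4 shifts range from -86% when palmitate is divided by same-day water to +77% when it is divided by time-averaged water. Neither document names either derivation. The range shows that the sign is unknown; it does not measure a defect.

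Unaffected are the between-arm null against pooled placebo, C4D15 against C1D1 when C1D1 is present, MRI-PDFF, sample size and safety. SAP 6.10.3 classes the endpoint as exploratory and its analysis as generally descriptive.

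**What to change.** Add to SAP 6.10.3.1:
- Hepatic DNL baseline is matched on days since first deuterated water: C1D-11 for C4D4, C1D-7 for C4D8, C1D1 for C4D15. A missing matched sample is not replaced by one from another labeling day.
- The matched baseline is the covariate in the mixed model. A baseline-by-visit term is optional with about 10 subjects per arm.
- C4D15 against C1D1 is the main DNL contrast.
- C4D22 has no run-in counterpart, so its change from C1D1 and the C4D15-to-C4D22 change are interpreted only as differences from pooled placebo.
- The DNL formula is given, including how body-water enrichment enters.
- Actual days since first intake are listed, because the visit windows make the matching nominal.

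The cost is SAP wording, one derived variable and one listing; every matched sample is already scheduled in Table 9-2.

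There are downsides. A subject without the matched sample drops out of that visit's change. Percent change is noisier on the smaller early baselines: under the model, C1D-11 is 0.98 to 0.65 of C1D1 for half-times of 0.5 to 2 days. Matching removes the within-arm offset but not the dilution of the early absolute between-arm contrast shown in Step 4, and the SAP should say so.
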